[name]
Professor of Fetal Medicine
The Newcastle upon Tyne Hospitals
NHS Foundation Trust
[name]
[contact]

Norwich

[name]
Consultant Obstetrician
Norfolk and Norwich
University Hospitals
NHS Foundation Trust
[name]
[contact]

Nottingham

[name]
Consultant Obstetrician
Nottingham University Hospitals NHS Trust
[name]
[contact]

[name] (lead Queens Medical Centre)
Consultant in Obstetrics and Maternal Fetal Medicine
Nottingham University Hospitals NHS Trust
[name]
[contact]

Sheffield

[name]
Consultant Obstetrician and Senior Lecturer
in Feto-Maternal Medicine
Sheffield Teaching Hospitals NHS Founda-
tion Trust
[name]
[contact]

Stoke

[name]
Consultant in Feto-maternal Medicine
University Hospital North Staffordshire
[name]
[contact]

Study Summary

The aim of this research study is to assess magnetic resonance (MR) imaging as a technology to aid in the prenatal diagnosis of fetal developmental brain abnormalities. The study will recruit at least 750 pregnant women from 18 weeks gestation onwards where the fetus is known or suspected of having some form of developmental brain abnormality based on antenatal ultrasound (US) examination. Study participants will be consented from at least 13 collaborating fetal medicine units drawing from a large and varied geographic and socio-economic referral area in England and Scotland. The study is designed primarily to assess the diagnostic accuracy of MR imaging (compared to the diagnostic accuracy of US alone), along with the related aspect of diagnostic confidence. This will be determined by comparing prenatal diagnosis with an anatomical reference diagnosis gained from either post-natal imaging in live born infants (up to 6 months of age) or post-mortem examination in the event of fetal demise, termination of pregnancy (TOP), stillbirth or early neonatal death. Figure 1 in the study design section of the protocol provides an overview of the study.

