- 2) All diagnoses revised (as above)
- 3) The number and proportion of cases where management intent is changed as a consequence of information made available by MRI, classified by gestational age (prior to 22 weeks, between 22 and 24 weeks, and after 24 weeks gestation).

5. Selection and withdrawal of participants

Inclusion Criteria

A participant is eligible for the trial if the following criteria are met:

1. Has an ongoing singleton or multi-fetal pregnancy of at least 18⁺⁰ weeks gestation* by ultrasound dating.
2. Is thought to be carrying a fetus with a brain abnormality following detailed specialist ultrasound examination.

Exclusion Criteria

A participant is excluded from the trial if any of the following criteria are met:

1. Inability to give informed consent.
2. Has a cardiac pacemaker, intra-orbital metallic foreign body, or recent surgery with metallic sutures or implant.
3. Has previously experienced or is likely to suffer severe anxiety or claustrophobia in relation to MR imaging examination.
4. Is unable or unwilling to travel to Manchester, Belfast, Birmingham, Leeds, Newcastle or Sheffield for specialist MR imaging.
5. Is unable to understand English (except where satisfactory translation services are available).
6. Is under the age of 16 years.

* It is a requirement that MR scans are not carried out prior to 18 weeks gestation. Women can be consented at 17 weeks gestation where there is a continuing pregnancy and they will be 18 weeks at the time of the MR examination.

Withdrawal Criteria

Withdrawal from the Study

1. Participant wishes to withdraw from the study.

6. Enrolment

All participants will be recruited by a fetal medicine specialist following an ultrasound scan which has identified a known or suspected brain abnormality in their fetus. In all cases, the fetal medicine specialist would complete non-patient identifiable details (see Appendix, Form A). In cases where the woman is eligible to enter the study, but the fetal medicine specialist does not feel it would be clinically appropriate or would introduce unnecessary delay in management, then details of the case and the reasons for not offering MR examination would be recorded on this form. An inclusion/exclusion checklist would then be completed for any woman who has indicated interest in the study. The specialist would give the

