Within 12 months of the initial fetal medicine consultation the fetal medicine specialist, or another member of staff from the fetal medicine clinic with prior knowledge and involvement in the case, will request relevant medical and maternity records for the collection of outcome data. In some circumstances this may require contact with the participant herself, particularly for live-births where paediatric case notes have not been located, or where there has been a change of address, hospital or consultant. The specific data to be collected will vary depending on the known outcome of the pregnancy (see Appendix, Form H).

A number of methods are available to allow research midwives to gather information about where and when women enrolled in the study deliver their baby. An "alert" sticker can be placed on the woman's maternity notes requesting that the delivering midwife notifies the MERIDIAN research midwife of the pregnancy outcome. A pro forma sheet (see Appendix, Form X) with pre-paid return envelope can also be given to the woman to be kept along with her handheld pregnancy notes; this could be done at one of their fetal medicine clinic visits or alternatively the sheet could be posted to the woman closer to the time of delivery where appropriate. The sheet can then be filled in after delivery by the woman herself or given to a relevant health professional for completion (labour ward midwife, reviewing paediatrician, obstetrician or community midwife). The sheet itself requests delivery details and also any known plans for neonatal follow up. These details can then be posted, faxed or phoned through to the research midwife. Using the delivery details gathered in this way the research midwife should be able to request outcome information a few months later (including results of postnatal imaging) from the relevant hospital department and clinician.

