The principal sensitivity analysis will examine the possible impact of repeat ultrasound, prior to possible MRI, on costs and outcomes. The likely impact of repeat ultrasound will be estimated based on the original ultrasound diagnosis, the information about the true status of the fetus obtained within the study, and combined with the existing literature and clinical expert opinion. Further sensitivity analyses will consider how travel costs may be reduced if MRI is offered at centres closer to parents' homes. This will be approximated by calculating the reduction in distance to hospital given other configurations of services, and reducing travel costs proportionately.

Finally, we will perform value of information analyses in order to identify those areas of uncertainty that may warrant further investigation.

Lost to Follow-Up

Where contact with a participant has not been successfully maintained during the study, she will be considered "lost to follow up" after one final attempted contact by telephone at 6 months following delivery (for livebirths only). This contact will only be attempted if it has not been possible to locate the necessary medical, maternity or paediatric records required for outcome data collection (in particular the outcome reference diagnosis which is drawn from postnatal imaging results). If this contact is required it will be made by the fetal medicine clinician or a midwife who has been involved with the participant's recent/ongoing clinical care. In cases of termination of pregnancy, fetal demise or perinatal death, post mortem examination results will be sought from medical records. If, for any reason, the results of a post mortem examination cannot be located within 6 months of the examination being completed, this case will be considered "lost to follow up". No further attempt will be made to contact the participant under these circumstances.

Wherever an outcome reference diagnosis is not available at the end of the 6 month period of follow up, all such cases will be retained in the study analysis of changes in fetal prognosis and management, but it will not be possible to include them in the analysis of diagnostic accuracy.

Study Safety

The following section outlines the methods for ensuring and assessing participant safety:

Definitions:

Adverse Event (AE): Any untoward medical occurrence in a subject.

Serious Adverse Event (SAE): Any adverse event such that it:

- results in death

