however, the details will be reported to the DMEC in order to judge whether this SAE would be likely to recur among future study participants and any necessary action to prevent this would be taken (for instance feedback to MR radiologists reporting such studies or specific modification of inclusion/exclusion criteria). The converse situation where in utero MR provides information which improves the fetal prognosis relative to the pre-existing prognosis based on ultrasound alone would be an AE rather than an SAE, but is still clinically very important. In this situation a woman may opt to continue a pregnancy based on false reassurance from the in utero MR examination. It is quite likely that ongoing monitoring of these pregnancies with ultrasound (or indeed a repeat MR) would highlight any such diagnostic error, but this would necessarily involve a delay in management and would be likely to affect clinical and legal aspects of the termination of pregnancy. Again, any such cases would be reported to the DMEC when first identified.

Further details of safety reporting are specified within the MERIDIAN Serious Adverse Event standard operating procedures document (see Appendix).

9. Statistics

Sample size

The study will recruit at least 750 pregnant women of gestational age 18+ weeks, leading to 504 completed cases (and a sub-group target of 336 women whose management choice is determined by 24 weeks gestation, a key date within the law governing termination of pregnancy). Recruitment to the study will continue to the end of the recruitment period, even if the target of 750 has been met prior to that; this is to ensure we meet the target of 504, and 336 at the point of follow-up. Pregnancies less than 24 weeks gestation will be defined based on gestational age at the time the MR scan is performed.

[figure not shown]

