All committees are governed by Sheffield CTRU standard operating procedures. The TMG consists of the Chief and Principal Investigators, the qualitative researcher and key staff within the CTRU. The role of the TMG is to implement all parts of the trial and to act on the recommendations from the TSC and DMEC. The TSC consists of the Chief Investigator and key staff within the CTRU (all as non-voting members), an independent chair, at least 2 independent members and a consumer representative. The roles of the TSC are to provide supervision of the protocol and statistical analysis plan, provide advice on and monitor progress of the trial, to review information from other sources and to consider recommendations from the DMEC. The DMEC will consist of an independent chair and 2 independent members including a statistician. The DMEC has responsibility for monitoring the results provided by the trial statistician to the plan described in the trial protocol with reference to efficacy and safety, reviewing information from other sources, providing recommendations to the TSC on why the trial might be modified or discontinued in terms of ethics and safety and considering adverse events. The DMEC will review the interim statistical analysis.

The planned project timetable and milestones are summarised in figure 4.

Project month	9-24	25	26	27	28	29	30	31	32	33	34	35	36	37	38	39	40	41	42	43	44	45	46	47	48	49	50	51	52	53	54	55	56			
	Nov 11 - April 13	May-13	Jun-13	Jul-13	Aug-13	Sep-13	Oct-13	Nov-13	Dec-13	Jan-14	Feb-14	Mar-14	Apr-14	May-14	Jun-14	Jul-14	Aug-14	Sep-14	Oct-14	Nov-14	Dec-14	Jan-15	Feb-15	Mar-15	Apr-15	May-15	Jun-15	Jul-15	Aug-15	Sep-15	Oct-15	Nov-15	Dec-15			
Recruitment	█																																			
Follow up (9 months)																		█	█	█	█	█	█	█	█											
Data cleaning (3 months)																									█	█	█									
Database lock (1 month)																											█									
Data analysis (3 months)																											█	█	█							
Final report writing (4 months)																													█	█	█	█				
Completion date																																		*		

Figure 4 – study Gantt chart

11. Data handling and record keeping

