Updated text details and flow chart for project 2 to allow the BSID to be completed in other suitable clinics, as well as hospital and participants home

Section 6. Assessments and Procedure (page 14)

Updated to clarify that if GMFCS is to be parent completed then the adapted motor skills questionnaire will be used.

Section 7. Statistics (page 19 and 20)

BSID scores updated in line with the scores produced from the BSID III

Protocol amendments since Version 3.0

Section 3. Study Design (page 10)

Design flow chart updated to change terminology to telephone contact and to allow contact in clinics.

Section 5. Enrolment (page 12 and 13)

Terminology updated to 'research team' rather than research nurse. Updated to allow telephone contact to be a telephone call or text message. Consent procedure updated to allow face to face consent completion in clinics.

Process for sending a reminder letter or text message if completed consent not returned added.

Section 6. Assessments and Procedure (page 14)

Terminology updated for clarity and procedure for contacting in clinic added.

Study Summary

The MERIDIAN study assessed the diagnostic accuracy of in utero magnetic resonance (iuMR) imaging and ultrasound for the detection of fetal brain abnormalities. Between July 2011 and August 2014 832 participants underwent both ultrasound and iuMR, with the primary objective being to ascertain whether iuMR after Ultrasound (US) leads to more accurate diagnoses of brain abnormalities than US alone. The reference diagnosis (against which ultrasound and iuMR were compared) was the findings of post-natal imaging performed within 6 months (age-corrected for gestational age) or, in the case of fetal/infant demise, from post-mortem. Further details of the study are available in the clinical protocol [1].

Following on from this the MERIDIAN 2-3 year follow up study was funded to incorporate additional follow-up of its participants, specifically: i) to incorporate longer term outcomes observed over the first 2-3 years of life, and ii) to undertake a detailed neurodevelopmental assessment of infants.

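### Figure 4 closes follow-up 9 months after recruitment, but the full 6-month reference window and final contact need about 11 months for a live birth scanned at 18 weeks

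*Protocol*

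**What the plan says.** Four parts of the protocol bear on this.

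- **Timetable.** The Gantt chart in section 10 (Figure 4) labels the period after recruitment "Follow up (9 months". The bar starts in September 2014. Data cleaning, database lock (June 2015) and analysis come next.
- **Reference diagnosis.** The Study Summary takes it, for survivors, from "post-natal imaging in live born infants (up to 6 months of age"). The later 2-3 year follow-up protocol describes the same window as "findings of post-natal imaging performed within 6 months (age-corrected for gestational age"), which counts it from the due date.
- **Loss to follow-up.** Under Lost to Follow-Up in section 8, a woman is declared lost only "after one final attempted contact by telephone at 6 months following delivery (for livebirths only"). Cases with no reference diagnosis at the end of follow-up leave the accuracy analysis.
- **Who may be recruited, and until when.** The Study Summary says "The study will recruit at least 750 pregnant women from 18 weeks gestation onwards". Section 5 adds that "Women can be consented at 17 weeks gestation where there is a continuing pregnancy", with the scan itself at 18 weeks. Section 9 says "Recruitment to the study will continue to the end of the recruitment period, even if the target of 750 has been met prior to that", so early-gestation women can enter up to the last day.

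**The concern.** The follow-up bar looks shorter than the follow-up rules it has to accommodate. A woman scanned at 18 weeks is still about five months from delivery, and the protocol's last outcome step comes six months after that.

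If the chart is followed literally, the final contact for the last early-gestation recruits falls after follow-up has closed. For the earliest scans it falls after the database has been locked. Any live-born infant not imaged by then drops out of the primary accuracy analysis, or is judged against a third-trimester ultrasound.

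The shortening is not spread evenly. A termination soon after an early scan leads to post-mortem well inside nine months. The imaging window that closes early belongs to live births scanned early, many of them in the under-24-week subgroup that carries the target of 336.

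**Working it through.** **Inputs**
- Follow-up after recruitment: 9 months (Figure 4 label; I do not rely on a count of drawn cells).
- Earliest scan: 18 weeks (Study Summary, section 5).
- Window and final contact: 6 months (Study Summary; section 8, Lost to Follow-Up).
- Last scans: August 2014 (Study Summary of the 2-3 year follow-up protocol), which agrees with a follow-up bar starting in September 2014.
- Lock: June 2015 (Figure 4).
- Delivery at 40 weeks: my assumption, as the documents give no term. I use 37 weeks, the protocol's preterm threshold in Table 2, as the lower end.
- Weeks per month: 365.25 / 12 / 7 = 4.348.

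**Formula.** Months needed = (delivery week − scan week) / 4.348 + 6. Infant age at close = 9 − (delivery week − scan week) / 4.348.

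**The plan's own figure.** The protocol gives no derivation of 9 months. It equals 3 months to delivery plus 6 months. With delivery at 40 weeks this fits a scan at 40 − 3 × 4.348 = 27.0 weeks; with delivery at 37 weeks it fits a scan at 24.0 weeks. Neither delivery week gives 9 months for an 18-week scan.

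**Delivery at 40 weeks**

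| Scan (weeks) | Months to delivery | Months to 6 months of age | Infant age at 9 months | Shortfall (months) |
|---|---|---|---|---|
| 18 | 5.06 | 11.06 | 3.94 | 2.06 |
| 20 | 4.60 | 10.60 | 4.40 | 1.60 |
| 22 | 4.14 | 10.14 | 4.86 | 1.14 |
| 24 | 3.68 | 9.68 | 5.32 | 0.68 |
| 27 | 2.99 | 8.99 | 6.01 | none |

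**Variants for the 18-week scan**
- Delivery at 37 weeks: 19 / 4.348 + 6 = 10.4 months. If the window is age-corrected, this relief applies to the telephone contact but not to the imaging window.
- Counted from consent at 17 weeks: 23 / 4.348 + 6 = 11.3 months.
- Collection allowed to run through cleaning and lock to the end of June 2015: 10 months, infant age 10 − 5.06 = 4.9 months, still under 6. Ten months is enough only from 40 − 4 × 4.348 = 22.6 weeks.

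**Calendar.** A scan on 31 August 2014 at 18 weeks gives delivery on about 1 February 2015 and a 6-month contact on about 1 August 2015. Nine months of follow-up ends on 31 May 2015.

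**How many women.** All of this is approximate and assumes uniform accrual.
- Accrual: 832 women over July 2011 to August 2014 (38 months) = 21.9 per month.
- Share scanned before 24 weeks: 336 / 504 = 2/3, the planned ratio.
- Survival: about 500 of 832 = 60%, from the follow-up protocol's sample size for Project 2.
- Mean shortfall for scans at 18 to 24 weeks: (2.06 + 0.68) / 2 = about 1.4 months. Then 21.9 × 1.4 × 2/3 × 0.60 = about 12.
- Upper bound using the largest shortfall: 21.9 × 2.06 × 2/3 × 0.60 = about 18.

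These are live births with a shortened window, not lost cases. The documents do not allow the number still unimaged at close to be estimated.

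**The case against.** **Six months is a limit, not a visit.** A reader might infer that a woman needs 11 months to obtain a reference diagnosis, or that the last live births are cut off. The documents do not support either reading. The window opens at birth, and even the worst case has about 3.9 postnatal months. Section 8 expects most scans to be done in routine care. It offers a study scan where none is planned by 2 months of age, leaving about 1.9 months to arrange it. This objection stands and limits the consequence.

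**The 12-month rule is not contradicted.** A reader might set "Within 12 months of the initial fetal medicine consultation" against the 9-month bar. It is a deadline for requesting records, and nine months meets it.

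**There are backstops.** A third-trimester ultrasound may serve as the reference, section 9 already allows for 10% losses and about 20% incomplete cases, and the follow-up study revisits case notes later. These protect power. They do not remove the conflict: an ultrasound reference shares its modality with one of the two tests compared, and the later study comes after the main lock.

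**A Gantt chart is not a follow-up rule.** It does not say that collection stops when the bar ends, and the final contact is needed only where records cannot be found. That is fair, but no passage says collection continues past the bar or that late recruits are handled differently, and lock is a firm stop.

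**The numbers are small.** A reader might divide the affected recruits by 336. That would be wrong, because 336 counts completed cases and not recruits.

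**Conclusion.** The inconsistency is real but modest. For live births scanned before about 27 weeks in roughly the last two months of recruitment, Figure 4 closes follow-up before the 6-month imaging window ends and before the final contact in section 8 is due. The shortfall is at most about 2.1 months. For the earliest scans the contact also falls after lock.

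Roughly 12 to 18 women in the under-24-week subgroup would have a shortened window, and fewer would lose their postnatal reference. That range rests on uniform accrual, two-thirds scanned before 24 weeks, about 60% survival and delivery at 40 weeks. Lower survival among early-scanned pregnancies would reduce it.

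The effect on power is small. The point deserves correction because the shortening falls on early-scanned live births only, and because a step the protocol itself requires cannot be carried out on its own timetable.

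**What to change.** Reconcile the Study Summary, Lost to Follow-Up in section 8 and Figure 4 to one closing rule. Outcome collection stays open until the last live-born infant has passed the 6-month window and the final contact, about 11 months after the last MR scan. State whether the 6 months run from birth or from the due date. Lock the database after that point, and clean closed cases in parallel.

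The cost is a lock up to about two months later, part of which parallel cleaning can absorb. No extra participants or procedures are needed. If the later lock is not affordable, the protocol should say how the last early-scanned live births are handled and report how many had no postnatal imaging at close.

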Appendix

Add-on study

Introduction

There are two elements to this add-on study to MERIDIAN, both of which have been supported by the NIHR-HTA. The first relates to the need to describe the False Negative Rate of ultrasonography as performed by an experienced feto-maternal expert (study A₁). Recruitment into MERIDIAN includes only fetuses thought to have brain abnormalities on ultrasound so the false negative rate cannot be estimated by the main MERIDIAN study. The second study will calculate the rate of unexpected brain abnormalities (i.e. not shown on ultrasonography) in fetuses with non-CNS abnormalities (Study A₂). The results of both studies will be of great potential importance to the NHS.

In both studies we plan to recruit 200 women whose fetus has had a detailed anomaly ultrasound by a feto-maternal expert which showed no brain abnormality. If a woman has had a previous pregnancy complicated by a brain abnormality the women will not be invited into the study. If participant numbers are not sufficient from this group we intend to recruit pregnant women from the general population who have not had a detailed anomaly ultrasound and arrange a fetal brain ultrasound with a fetal medicine consultant as part of the study.

Aims and Objectives

Study A₁

The aim is to answer the question:

What is the false negative rate of ante-natal ultrasound performed by feto-maternal experts when trying to detect fetal brain abnormalities?

Study A₂

[figure not shown]
The aim is to answer the question:

What is the rate of unexpected brain abnormalities detected by iuMR imaging in fetuses with known non-CNS abnormalities.

Study Design

Participants will be recruited via option 1. Option 2 will be held in reserve and only used if recruitment via option 1 is insufficient.

Participant pathway diagram Option 1:

Participant pathway diagram Option 2:

Initial identification of participant

- Pregnant women whose pregnancy is normal are sought through:
 - Scanning ultrasound clinics at participating MERIDIAN sites
 - Charitable organisations working in pregnancy, working within the Sheffield area
 - Community midwives in Sheffield area
 - GP lists in Sheffield area
 - Local media
- Participants are given a patient information leaflet and or information sheet and details of how to register their interest in taking part in the study (phone/email)

Screening (telephone call with participant)

- Department of academic radiology has contact with participant
- If participant is still interested in the study they will be asked screening questions
- Date for Ultrasound and MRI scan arranged
- Full patient information sheet sent to participant (if not already received)

Detailed Ultrasound & MRI visit (visit to academic Unit of radiology in Sheffield)

- Participant visits academic of radiology department,
- consent taken, including permission for scan results to be sent to GP
- Brain ultrasound performed
- MRI scan performed
- Participant offered MR image of baby to keep and £10 voucher.

Post MRI activities (no participant contact required)

- Results of Ultrasound & MRI scan sent to GP

Inclusion Exclusion Criteria

Inclusion Criteria

A participant is eligible for the trial if the following criteria are met:

For study A1

1. Has an ongoing singleton or multi-fetal pregnancy of at least 18⁺⁰ weeks gestation* by ultrasound dating.
2. Is thought to be carrying a fetus with no abnormality whatsoever (i.e. no brain or somatic abnormality) **

For study A2

1. Has an ongoing singleton or multi-fetal pregnancy of at least 18⁺⁰ weeks gestation* by ultrasound dating.
2. Is thought to be carrying a fetus with no brain abnormality but does have a confirmed somatic abnormality **

* It is a requirement that MR scans are not carried out prior to 18 weeks gestation. Women can be consented at 17 weeks gestation where there is a continuing pregnancy and they will be 18 weeks at the time of the MR examination.

** if recruited via option 1 this criterion will be based on a normal mid pregnancy anomaly scan in a fetal medicine centre. If recruited via option 2 this will be self-reported by the participant based on their medical care to date e.g. screening ultrasound

Exclusion Criteria

A participant is excluded from the trial if any of the following criteria are met:

1. Has a past history of a fetal brain anomaly in a previous pregnancy
2. Inability to give informed consent.
3. Has a cardiac pacemaker, intra-orbital metallic foreign body, or recent surgery with metallic sutures or implant.
4. Has previously experienced or is likely to suffer severe anxiety or claustrophobia in relation to MR imaging examination.
5. Is unable or unwilling to travel to Sheffield or attend St George's Hospital for specialist MR imaging.

6. Is unable to understand English (except where satisfactory translation services are available).
7. Is under the age of 16 years.
8. Is unwilling for GP to be informed about the study and given copies of scan reports

Withdrawal Criteria

- Participant wishes to withdraw from the study.
- Participant was ineligible at the time of consent

Study Treatment (antenatal MRI)

As per main protocol.

Assessments and procedures (option 1 pathway)

Enrolment (option 1 pathway)

Participating MERIDIAN sites will have posters and leaflets in public areas with details of the sub study. Potential participants can then ask staff about the study and receive the full participant information sheet. Also Fetal Medicine specialists can tell women in clinic about the study and give them the full patient information sheet. Women who are given the PIS in person should be asked if they are willing to be contacted by the academic radiology to discuss the study further. In addition clinic lists can be screened and women who have had a detailed ultrasound anomaly scan within the last seven days can be sent a patient information sheet by post.

Staff at the academic unit of radiology or St George's Hospital (for St George's referrals only) will then have a telephone conversation with potential participants and ask them some screening questions. Eligible participants will be offered an appointment for an MRI scan at the academic unit of radiology or St Georges Hospital. If the participant has not had the full patient information sheet this will be sent to them either via email or post. Travel expenses for the participant and partner/friend/relative will be made available. When they attend the appointment informed consent will be taken. An important part of the consent procedure is the willingness of participants to allow their GP to be informed that they are taking part in the study and have a copy of the MRI report (see safety section).

Women in study A2 who are carrying a baby with a suspected non-brain abnormality will be given a supplementary information sheet which clearly states that scanning will be for the brain only. This is covered briefly in the main patient information sheet but we feel it important to emphasise this aspect of the study to this particular group of participants.

The enrolment procedure will be optimised to minimize the time between the ultrasound scan and MRI scan. Potential participants will be telephoned promptly once their details have been received and be offered the earliest available MRI appointments. Ideally an MRI

would be take place within one week of the ultrasound, but participants will still be accepted regardless of the interval between ultrasound and MRI.

Study Visit (option 1 pathway)

Participants will attend a clinic at the academic unit of radiology or St George's Hospital. Informed consent will be taken.

After consent background information about the participant will be recorded by staff.

The participant will have the MRI scan and be offered an image of the baby to keep. Participants will also be offered a £10 voucher . Normally the participants will be able to have a discussion about the results of the scan and be given some immediate feedback, the participants will be reminded that results are going to be sent to their GP.

No further patient contact is required after this visit.

Post Visit activities (option 1 pathway)

After the visit a copy of the MRI report will be sent to the participant's GP and their consultant if they are still receiving care from a fetal medicine unit.

A copy of the detailed anomaly ultrasound report will be requested from the referring MERIDIAN centre (unless the participant had a copy in their hand held maternity notes, if this is the case a copy of the report from the maternity notes will be used).

Assessments and procedures (option 2 pathway)

Enrolment (option 2 pathway)

Participating MERIDIAN sites will be able to identify participants as for option 1, but to a wider group of patients who have not had an ultrasound by a fetal medicine consultant.

In addition suitable organisations working in Sheffield and surrounding areas such as Charitable organisations working in pregnancy, Community midwives, GPs will be approached and asked if they will make information about the study available to pregnant women they work with. Potential participants will have access to participant flyer and full information sheet. The participant flyer will have phone and email contact details for Academic Unit of radiology and participants can register their interest.

Staff at the academic unit of radiology will then have a telephone conversation with potential participants and ask them some screening questions. Eligible participants will be offered an appointment for an ultrasound and a MRI scan at the academic unit of radiology. Travel expenses for the participant and partner/friend/relative will be made available. When they attend the appointment informed consent will be taken. An important part of the consent procedure is the willingness of participants to allow their GP to be informed that they

are taking part in the study and have a copy of the Ultrasound and MRI reports (see safety section).

Women who are carrying a baby with a suspected non-brain abnormality will be given a supplementary information sheet which clearly states that scanning will be for the brain only. This is covered briefly in the main patient information sheet but we feel it important to emphasise this aspect of the study to this particular group of participants.

Study Visit (option 2 pathway)

Participants will attend a clinic at the academic unit of radiology. Informed consent will be taken.

After consent background information about the participant will be recorded by staff.

The participant will have a fetal brain ultrasound with a fetal medicine consultant. If the ultrasound shows normal brain development the participant will go on to have the MERIDIAN Add on study MRI scan. If the ultrasound detects a suspected brain abnormality the fetal medicine consultant will counsel the participant based on the anomaly seen and advise her to see her GP. The patient will have no further data collected for the MERIDIAN study. If it would be beneficial a clinical MRI will be offered to be done immediately during the same visit. This MRI will not be reported as part of the MERIDIAN Add on study.

The participant will then have the MRI scan and be offered an image of the baby to keep. Participants will also be offered a £10 voucher. Normally the participants will be able to have a discussion about the results of the scan and be given some immediate feedback, the participants will be reminded that results are going to be sent to their GP. No further patient contact is required after this visit.

Post Visit activities (option 2 pathway)

After the visit a copy of the scan reports will be sent to the participant's GP.

Safety

Only adverse events that occur during the MRI scan will be captured. There will be no participant follow up as part of this study.

The reports of scans performed for this study will be sent to the participant's doctor(s), in some cases this will be a GP in other cases a consultant. If an anomaly is detected it will be the doctor's responsibility as part of his or her normal clinical care to take appropriate action.

Statistics

Starting from the assumption that no US false negatives will be found, the extension study will recruit 200 fetuses in each group. This figure has been derived from the $3/n$ rule (Eypasch et al., 1995), a large sample approximation of the upper 95% confidence interval for very rare events. If no adverse events are observed in a sample of size of n , this does not

imply that adverse events are impossible; instead, a confidence interval can be constructed to quantify the upper limit of the event rate. The study will therefore estimate the negative predictive value of US to an upper limit of 3/200 or 1.5% in the absence of false negatives. If false positives are encountered, the study will estimate the negative predictive value to a standard error of $\leq 2\%$ for plausible occurrence rates (i.e. $<10\%$).

Reference

MERIDIAN – 2-3 year follow up study

Funded by the National Institute for Health Research's Health Technology Assessment programme (project number 09-06-01)

Magnetic resonance imaging to enhance the diagnosis of fetal developmental brain abnormalities in utero - 2-3 year follow up study

[name]
Academic Unit of Radiology
University of Sheffield
[name]
Royal Hallamshire Hospital
Sheffield
[name]

[name] (tel)
[name] (fax)

[contact]

www.shef.ac.uk/meridian

RESEARCH PROTOCOL
(Version 4.0) 28th September 2016

Sheffield CTRU ref	URMS 144460
CSP	180504
STH R&D ref	STH19125
NIHR HTA ref	09-06-01
Ethics ref	15-YH-0398
ISRCTN	ISRCTN27626961

Authorised by: [name]

Magnetic resonance imaging to enhance the diagnosis of fetal developmental brain abnormalities in utero – 2-3 year follow up study

MERIDIAN

Contents

Study Summary.....	6
1. Introduction.....	7
2. Aims and objectives	8
3. Study Design.....	9
4. Selection and withdrawal of participants	11
5. Enrolment.....	12
6. Assessments and procedures.....	13
7. Statistics	19
